## **4.0 Number of Subjects**

The proposed single-site study will be conducted at The Ocular Surface Institute at the University of Houston College of Optometry. Up to 76 subjects will be screened for study inclusion, with the goal of completing 34 subjects.

Source data will be collected on paper case report forms and then doubly entered electronically into a database by trained personnel. Source data will be quality assured at the levels of coding, scoring, and entry prior to locking the dataset for analysis.

In this within-subject crossover design, a paired t-test will be used to compare primary outcome visual acuity performance of study treatment lens wear to standard spherical contact lens wear among astigmats. We will use a two-sided independent t-test to ensure there are no carry over or period effects in our cross-over design, although it is not anticipated. As a secondary outcome, subjects will be asked their preference of contact lenses in a two-alternative forced choice format. A one-sample binomial test will be used to test the hypothesis that the probability of preference to treatment lens and standard lenses are equally likely ( $H_0: p=.5$  v.  $H_1: p\neq.5$ ).

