## FULL PROTOCOL TITLE: Toric Contact Lens Performance Study

We aim to test the hypothesis that  $H_0: \Delta=0$  v.  $H_1: \Delta\neq0$  using a two-sided test with significance level  $\alpha=0.05$ , where  $\Delta$  is the underlying benefit for treatment contact lenses versus spherical contact lenses in this cross-over design. Based on previous studies reported average photopic low contrast visual acuity ranged from 0.3 to 0.4 logMAR with various brands of toric contact lenses and under the same conditions from 0.51 to 0.56 with spherical contact lenses among low-to-moderate astigmatic eyes. An estimated improvement with toric lenses has been reported as  $0.07\pm0.14$  among those with low astigmatism with the magnitude of improvement increasing among those with high levels of astigmatism. It is reasonable to expect a detectable range of 2 letters to half-line of improvement with the treatment contact lenses versus the standard sphere lenses. If we expect a half-line treatment benefit and the within-subject variance of the difference in mean visual acuity between the two periods to be a line (0.1 logMar), then based on pilot-study results, and a required 80% power we need 34 participants overall for each study population (68 total). We will randomize an equal number of subjects to each group (i.e., group A receives treatment 1 in period 1 and treatment 2 in period 2; group B receives treatment 2 in period 1 and treatment 1 in period 2). Depending on the variability, a sample size of 34 in each sampled population allows us to detect a smaller effect size (e.g., high contrast tests) as low as 2.5 letters with a within-subject variability of 0.06 logMar. The visual function testing is novel and has not been used on a population of astigmatic contact lens wearers. So sample size planning cannot be done for these tests. We plan to screen up to 38 participants from the study population to allow for attrition.

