## 6.0 Study Endpoints

The primary study endpoints will compare toric to spherical lenses for:

- Binocular near visual acuity

The secondary study endpoints will compare toric to spherical lenses for:

- Binocular near visual performance
  - Reading speed, errors, etc.
- Contrast
  - Binocular low contrast acuity, contrast sensitivity at near

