1.1.16	Contact Lens Fitting	
Fit subject in the first set of contact lenses based on randomization schedule.
 
 
• The toric lens parameters should be selected based on the manufactures fitting guide.
 
• The powers for the spherical lenses should be the vertexed spherical equivalent.
 
 
After allowing the lens to settle for 10 minutes, assess the fit using slit lamp biomicroscopy.

1.1.17	Contact Lens Over-Refraction	
Perform over-refraction using maximum plus to best visual acuity
 
 
• Perform best sphere and spherocylindrical over-refraction
 

1.1.18	Contact Lens Power Adjustment (if necessary)	Follow the manufactures fitting guide and modify contact lens power, based upon the Contact Lens Over-Refraction, if the subject gains more than 3 letters of acuity with over-

**FULL PROTOCOL TITLE:** Toric Contact Lens Performance Study

		refraction
--	--	------------

Visit 2: Contact Lens Follow Up Lens #1		
Note: Subjects should report wearing their assigned study contact lenses at least 2 hours.		
2.1	Visual Acuity	Perform Distance Snellen acuity OD/OS with the patient's study lens correction.
2.2	Contact Lens Assessment	Assess the fit using slit lamp biomicroscopy.
2.3	Contact Lens Over-Refraction	Perform over-refraction using maximum plus to best visual acuity
2.4	Contact Lens Power Adjustment (if necessary)	Follow the manufacturer's fitting guide and modify contact lens power, based upon the Contact Lens Over-Refraction, if the subject gains more than 3 letters of acuity with over-refraction 

• Perform best sphere and spherical-cylindrical over-refraction

2.5	Slit Lamp Exam with NaFL	Remove the contact lens and instill NaFL then evaluate slit lamp findings using the CCLRU grading scale

Visit 3: Outcome Lens #1		
Note: Subjects should report wearing their assigned study contact lenses at least 2 hours.		
3.1	Visual Acuity	Perform Distance Snellen acuity OD/OS with the patient's study lens correction.
3.2	Questionnaires	Administer the NAVQ to the subject
3.3	High and Low Contrast Near Visual Acuity	Measure logMAR high and low contrast acuity at near OU with high luminance
3.4	Contrast Sensitivity	Perform the contrast sensitivity test on the iPad
3.5	Radner reading test	Perform the Radner reading speed test on the iPad

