5.7	Slit Lamp Exam with NaFL	Remove the contact lens and instill NaFL then evaluate slit lamp findings using the CCLRU grading scale
5.8	Study Exit	Ensure all paperwork is complete and

**FULL PROTOCOL TITLE:** Toric Contact Lens Performance Study

	exit the subject from the study.
--	----------------------------------

Layman's Description of Procedures	
Patient demographics	The subjects will be asked questions about their age, sex, race and ethnicity.
History	The subjects will be asked questions about their systemic and eye health and surgical history. The subjects will be asked questions about how they use their current contact lenses, such as their current contact lens brand and wear time, as performed during a normal eye exam.
Concomitant Medications	The subjects will be asked questions about their current ocular and systemic medications.
Visual acuity and contrast sensitivity	Measurements of how well subjects can detect letters/lines and with varying levels of contrast (black versus grey on light background)
Auto-refraction/keratometry	A machine will shine light into a subject's eye and will estimate their prescription and curvature of the eye without making contact with the eye.
Slit Lamp Exam	A specialized microscope is used to shine light on the eye and to examine the health of the front of the eye. Sodium fluorescein (NaFl) is a temporary dye that is used in routine contact lens exams to evaluate the health of the front surface cells.
Refraction	The subject's prescription is determined by placing different power lenses in front of the subject's eye, and modified according to the subject's responses.
Contact Lens Fitting	A contact lens is placed on the eye and the fit is assessed (how much it moves, where it sits on the eye, etc.). This is done using a slit lamp biomicroscope.
Contact Lens Over-Refraction and Power Adjustment	Lenses will be placed in front of the subject's eye while wearing the study contact lenses to determine if the prescription needs to be changed according to the subject's responses. The contact lens power will be adjusted if needed based on standard clinical fitting guidelines.
Questionnaires	Asks the subject about his/her vision
Radner Reading and functional vision tests	Measure reading performance (speed, accuracy, etc.) using an iPad based app.

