### **9.0 Drugs or Devices**

No investigational drugs or devices will be used in this study. The contact lenses fit in the study are commercially available, FDA approved contact lenses that will be worn on a daily wear, daily disposable basis. An assistant will mask (over-label) contact lenses so that the subject and outcome examiner remain masked. The primary examiner will follow the manufacturer's fitting guide to determine the initial lens powers. Lens powers will be modified, as needed for best vision, according to the manufacturer's fitting guide.

The ophthalmic dye used in the trial to evaluate the health of the front surface (sodium fluorescein) is a commercially available ocular diagnostic agent commonly used in routine clinical assessment of contact lenses in optometry.

Study Arm	Study Contact Lenses (Alcon)	Base Curve	Diameter
Toric/Astigmatic	Dailies Aqua Comfort Plus Toric	8.8	14.4
	Dailies Aqua Comfort Plus Sphere	8.7	14.0

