Title: Toric Contact Lens Performance Study

NCT number: NCT03546647

Document date:

Protocol: 27 Aug 2018

Statistical Analysis Plan:

The treatment effects on pre-specified outcomes that met the parametric assumptions were analyzed using the Grizzle model (Grizzle, 1965) for the two-period two-treatment crossover trial. First, the data were tested for the presence of a carry-over effect according to the sequence of randomization, that is, sphere or toric, during the first period at the critical level of 0.10. Then, the treatment effect was estimated using a linear mixed model in the presence of period and sequence effects to obtain unbiased effect sizes. For pre-specified outcomes that did not conform to non-parametric testing, Koch's approach using the Wilcoxon rank sum test was used. Treatment differences and 95% Confidence Intervals were estimated using the Hodges-Lehmann method. In the presence of any carry-over effects, hypothesis tests were conducted on period 1 only. Unadjusted p-values are reported and inferred using a specified critical region after adjusting for multiple testing. Summary measures of means and standard deviations are reported for variables conforming to parametric testing and median, 25th percentile, and 75th percentile were reported otherwise. A one-sample binomial test was used to test the hypothesis that the probability of subject preference to treatment lens and standard lenses are equally likely. The hypothesis that $H0: \Delta=0$ vs. $HH1: \Delta\neq0$ using a two-sided test with significance level $\alpha=0.05$ was tested, where Δ is the underlying benefit for treatment contact lenses versus spherical contact lenses in this cross-over design. To assess treatment differences in spatial frequency, a repeated measures model was used and tested for the interaction between spatial frequency and lens type. In the presence of a statistically significant interaction, follow-up testing with appropriate Type I error adjustment was used.

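### Outcome visits set only a self-reported 2-hour minimum of lens wear and no time of day, so a subject's two measurements may be taken under unmatched conditions; matching them is a cheap improvement with a probably small gain

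*Protocol*

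**What the plan says.** Protocol section 7.0 puts the same note above the procedures for Visit 3 and Visit 5: "Subjects should report wearing their assigned study contact lenses at least 2 hours". This is a minimum that rests on the subject's report. There is no upper limit, no target, and no instruction linking the second outcome visit to the first.

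The visit table in section 5.0 places the outcome visits at Day 10 ± 2 and Day 20 ± 2 and gives no time of day. Section 9.0 says the lenses are "worn on a daily wear, daily disposable basis", so reported wear at testing can run from 2 hours to a full day.

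None of the steps listed for Visits 3 and 5 is an entry for insertion time or hours worn. The only wear-time item described is the history of the subject's own lenses, "such as their current contact lens brand and wear time, as performed during a normal eye exam".

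The primary endpoint in section 6.0 is "Binocular near visual acuity". Section 4.0 plans that "a paired t-test will be used to compare primary outcome visual acuity performance of study treatment lens wear to standard spherical contact lens wear". The SAP instead states that "the treatment effect was estimated using a linear mixed model in the presence of period and sequence effects". Neither analysis includes wear time.

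**The concern.** Each lens has one outcome visit, so a subject's contribution to the primary comparison is one Visit 3 value set against one Visit 5 value. Pairing removes what is constant within a subject. It does not remove something that changes between that subject's two visits, such as hours since insertion or time of day. Period and sequence terms do not remove it either, because it varies from subject to subject within each period.

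The population makes this plausible. Section 3.0 requires at least 5 hours a day of digital device use, and the endpoints include near acuity, reading performance and contrast. A late-day test may follow hours of near work that a test 2 hours after insertion does not.

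Two things are at stake: some precision in a trial planned with almost no spare power, and the ability to show afterwards that the two lenses were tested under comparable conditions.

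**Working it through.** **Inputs from the protocol (section 4.0).** Benefit of half a line, 0.05 logMAR; 0.1 logMAR for what the text calls the "within-subject variance of the difference in mean visual acuity between the two periods"; 80% power; N = 34; and α = 0.05, "using a two-sided test with significance level".

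**Step 1. Reproduce N = 34.**
- Normal approximation: (1.96 + 0.84)² × (0.1/0.05)² ≈ 31.4, so 32.
- Paired t-test with the noncentral t distribution: the smallest n reaching 80% is 34.
- At n = 34 the noncentrality is (0.05/0.1) × √34 = 2.92. Power is 80.8% with 33 degrees of freedom and 80.7% with 32, as in a two-sequence crossover analysis.
- Read as a variance, 0.1 would give n = 316, so it acts as an SD.

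The stated size is right, with less than one point of power in reserve.

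**Step 2. Assumed spread of wear time.** The documents give none. Take hours worn at testing as uniform over 2 to 10 hours at each visit, independent between visits.
- SD at one visit = (10 − 2)/√12 = 2.31 h.
- SD of the between-visit difference = √2 × 2.31 = 3.27 h.

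**Step 3. If this noise is additional to the planned SD.** With slope b in logMAR per hour (assumed), SD of the difference = √(0.1² + (b × 3.27)²). Power is at n = 34 with 32 degrees of freedom.

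| Assumed b | b × 3.27 | Share of 0.1² | Total SD | Power |
|---|---|---|---|---|
| 0 | 0 | 0% | 0.1000 | 80.7% |
| 0.003 | 0.0098 | 1.0% | 0.1005 | 80.3% |
| 0.005 | 0.0163 | 2.7% | 0.1013 | 79.7% |
| 0.010 | 0.0327 | 10.7% | 0.1052 | 76.7% |

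**Step 4. If wear times are less variable.** With a within-subject correlation of 0.5 (assumed), the SD of the difference is 3.27 × √0.5 = 2.31 h, and power at the three slopes is 80.5%, 80.2% and 78.7%. With wear over 2 to 6 hours and independence, it is 80.6%, 80.4% and 79.7%.

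**Step 5. If the planned SD already contains this noise.** Complete matching would reduce the SD to √(0.1² − (b × 3.27)²), that is 0.0995, 0.0987 or 0.0945. Power at n = 34 becomes 81.1%, 81.7% or 84.9%.

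**Step 6. Bias.** If wear has the same distribution with both lenses, as in steps 2 to 5, the expected shift in the mean difference is zero. A shift arises only if mean hours worn differ by lens, and then equals b times that difference. The documents give neither quantity.

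**The case against.** The case against is substantial. At the low and middle slopes the power loss is 0.4 and 1.0 points, and only the top slope costs 4 points. No slope comes from the documents, and independence between visits is pessimistic, since the same person attending the same clinic may well come at similar hours. Section 4.0 also refers to pilot results, so ordinary visit-to-visit variation may already be inside the 0.1. All of this stands, and it limits the size of the point.

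A reader might infer a serious bias: that a subject who sees poorly with the spherical lens would insert it late and wear the toric lens all day. A 4-hour gap at 0.010 logMAR per hour would shift the estimate by 0.040 logMAR, or 80% of the half-line target. The documents do not support this. Both the gap and the slope are assumed. The 2-hour minimum applies to both lenses, subject and outcome examiner are masked, order is randomised, and lens power is checked by over-refraction at fitting and follow-up. Lens-dependent wear remains possible, because a masked subject can still notice vision or comfort, but nothing shows that it occurs.

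A reader might also infer a larger gain from matching. If unmatched wear made up 20% of the planned variance, power would rise to 88.5%. That needs a slope of √(0.2 × 0.01)/3.27 = 0.0137 logMAR per hour, above the range considered here.

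Nor do the documents show that wear time goes unrecorded. The case report forms are not included, and staff must ask about wear to apply the note. What can be said is that recording is not specified. The point also does not reach every endpoint as a paired difference: lens preference is a binomial outcome, and the SAP falls back on period 1 alone if carry-over is found.

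**Conclusion.** The point holds as a minor design improvement. The protocol lets a subject's two outcome measurements be taken at different hours of wear and times of day, and neither document matches, specifies recording of, or adjusts for this. The result is avoidable noise in the within-subject difference. Bias is a possibility only, conditional on wear before testing differing systematically by lens.

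On the assumed slopes and wear pattern, the cost is about 0.4 to 4 points of power (80.7% to between 80.3% and 76.7%), and less if wear times are correlated within subject. Alternatively, if the planned SD already includes this variation, there is an unused gain to about 81% to 85%. These ranges rest on assumptions and not on figures in the documents. The sample size calculation itself is not in error on this account.

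**What to change.** In the notes to Visits 3 and 5 in section 7.0:

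- keep the 2-hour minimum as it stands;
- book Visit 5 at about the same time of day as that subject's Visit 3, for example within 2 hours;
- ask the subject to insert the lenses at about the same clock time on both days;
- record insertion time and test time at steps 3.1 and 5.1.

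In the SAP, report hours worn at testing by lens. Any model that adjusts for hours worn should be labelled exploratory. Hours worn is measured after randomisation and may be affected by the lens, so adjusting for it could remove part of the lens effect or introduce bias.

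The cost is a short addition to each visit note, two time entries at each outcome visit, and a modest scheduling constraint on Visit 5. No extra visit, test or staff is needed.

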## 8.0 Setting

## **FULL PROTOCOL TITLE:** Toric Contact Lens Performance Study

All study visits will be conducted at the University of Houston College of Optometry in The Ocular Surface Institute (TOSI).

### **9.0 Drugs or Devices**

No investigational drugs or devices will be used in this study. The contact lenses fit in the study are commercially available, FDA approved contact lenses that will be worn on a daily wear, daily disposable basis. An assistant will mask (over-label) contact lenses so that the subject and outcome examiner remain masked. The primary examiner will follow the manufacturer's fitting guide to determine the initial lens powers. Lens powers will be modified, as needed for best vision, according to the manufacturer's fitting guide.

The ophthalmic dye used in the trial to evaluate the health of the front surface (sodium fluorescein) is a commercially available ocular diagnostic agent commonly used in routine clinical assessment of contact lenses in optometry.

Study Arm	Study Contact Lenses (Alcon)	Base Curve	Diameter
Toric/Astigmatic	Dailies Aqua Comfort Plus Toric	8.8	14.4
	Dailies Aqua Comfort Plus Sphere	8.7	14.0

### **10.0 Risks to Subjects**

The risks to the subjects in the trial are the same risks found in standard clinical practice and patients wearing contact lenses outside of a controlled trial. During study procedures, there is the risk of mild discomfort due to light being shined on the eye or through the use of topical ophthalmic diagnostic agents (sodium fluorescein) or insertion of contact lenses. Potential discomfort from these procedures is transient and self-limiting.

Contact lenses will be fit as part of this study. The US Food and Drug Administration consider daily wear contact lenses Class II medical devices. While most individuals wear contact lenses without problems, there are some risks associated with wearing contact lenses. Ulcerative keratitis (infection of the clear front part of the eye), is the most severe risk and can lead to loss of vision. Ulcerative keratitis is estimated to happen to about 1-2 out of 10,000 people who use daily wear, daily disposable contact lenses. The risk for ulcerative keratitis in this study is no different than the risk found with contact lens fitting in standard clinical practice. The risk of ulcerative keratitis may be reduced by educating subjects to carefully following the study doctor's directions for lens care, including throwing out your contact lenses each night, never sleeping or napping in contact lenses, and never exposing the contact lenses to water. These study instructions are the same as those provided to subjects in clinical practice.

In addition to ulcerative keratitis, the following problems may occur when wearing contact lenses:

## **FULL PROTOCOL TITLE:** Toric Contact Lens Performance Study

- Other, less serious, infections or inflammation of the eye(s)
- Burning, stinging, itching, dryness or general irritation of the eye(s)
- Corneal neovascularization (small blood vessels growing into the cornea)
- Excessive watering, unusual eye secretions, or redness of the eye
- Reduced or blurred vision (compared to glasses)
- Seeing rainbows or halos around bright lights (compared to glasses)

Many of the potential problems associated with contact lens wear are self-limiting and can be resolved with discontinuation of lens wear. These problems can be minimized or avoided with proper contact lens fitting and follow-up. Subjects in the study will be examined approximately 3-7 days after contact lens fitting, which is a typical follow-up schedule seen in clinical practice for contact lenses worn in a daily wear modality.

Subject safety will be monitored in the trial through slit lamp evaluation of the ocular surface. Subjects will be educated to potential risk with contact lens wear and instructed to discontinue contact lens wear and contact the study investigators immediately if they experience any eye discomfort, excessive tearing, vision changes, redness of the eye, or other problems.

Subjects will be instructed that in the event they experience signs or symptoms associated with a potential adverse event, they should contact the study personnel immediately for evaluation.

### **11.0 Potential Benefits to Subjects**

While there are few direct benefit to the study subjects, subjects will be unmasked (told what each of their study lenses were) at the end of the study. Through this they may learn more about their vision and visual performance with different types of contact lenses. Participation in the study may also improve the fitting of multifocal and toric contact lenses for future patients.

